Name (print):_____

Position:_____

Principal Investigator (PI):

Date:	dd	mmm	yy
-------	----	-----	----

Signature:_____

Name (print):_____

Position:_____

COVID-19 IMPACT STATEMENT

The proposed study design outlined in the following protocol will be appropriately implemented in line with current guidelines set out by the UK and Welsh Government for Coronavirus management. Up to date Government guidance will be followed throughout the study, which will potentially impact certain aspects of study conduct, as described in this protocol. Study visits will be conducted remotely while necessary, until such time where face-to-face visits are permitted to recommence. Key members of the study team will monitor relevant guidance for GP surgeries and hospitals closely and adjust study conduct accordingly, consistent with any new information and/or restrictions as it is released. Where study tasks are conducted remotely, recent HRA advice released for conducting clinical trials during COVID-19 outbreak will be adhered to, where applicable. Any study visits conducted in person will take place with all required precautions in place to prevent the spread of the virus. Due to the restrictions and guidance in place from the government, recruitment efforts designated to JCRF nurses in Swansea will be limited to screening of A&E databases at Morriston hospital and sending recruitment letters via secondary care where applicable/appropriate.

Additionally, the study acknowledges that the current pandemic of COVID-19 and resulting restrictions and dramatic changes to patient lifestyle has the potential to cause additional adverse impact on quality of life issues for the study population being investigated. Quality of life issues directly caused due to the global pandemic of Coronavirus will not be investigated as part of this study. However, anecdotal information will be collected about how patients manage their diagnosis of AF during relevant clinic closures, lockdown environment and social distancing restrictions.

SYNOPSIS

Protocol Title: Evaluating QUAlity of Life of AF patients following a bleed (EQUAL-AF)

Study Design:

A cross-sectional, observational feasibility study which will provide a descriptive evaluation of the quality of life (QoL) of atrial fibrillation (AF) patients experiencing a bleed, both in primary care and hospital settings (wards and emergency department (ED)). No control patients (i.e. no-bleed patients) will be enrolled as part of this feasibility phase.

Objective(s):

Primary objective

- To test the feasibility of identifying patients with both minor and major bleeds as a result of anticoagulant treatment for AF and evaluating their QoL through both primary and secondary care settings.

Secondary Objectives

- To describe and interpret the observed differences in QoL by type of bleed.
- To describe the treatment received and the nature of the bleed experienced by the patient.
- To undertake structured qualitative interviews to gain detailed insight into issues from a patient perspective, for those who live with AF and have experienced a recent bleed while taking anticoagulants.
- To observe appropriateness of three chosen PROMs (EQ5D, AFEQT and PACT-Q, part 2) in capturing QoL data, specifically post a bleeding event for AF patients who are taking anticoagulants.

Outcome measure(s):

Primary outcome measures

- The study will be considered feasible if recruitment efforts prove successful:
 - A sample size of 50-80 patients will be required for the study in line with the guidance outlined in the Lancaster et al (2004) publication regarding feasibility studies¹. A minimum of 50 patients recruited will deem the study as successful.

- Patient reported outcome measures (PROMs) will be used in the study using a survey design to collect QoL data from patients directly in both primary and secondary care settings. Three validated questionnaires will be used in this study: EQ5D, AFEQT and PACT-Q. All questionnaires have previously been used in atrial fibrillation studies to collect QoL data.

Secondary outcome measures

- Patients will be asked to provide their anticoagulant medication information along with full details of the bleed they have experienced, which will be used to later categorise the bleeds as minor or major by a medical professional, during the data cleaning and analysis. Medication and bleed details will be recorded before each patient completes the selected study PROMs.
- A sub-set of 10 patients will be asked to take part in a qualitative semi-structured interview, which will aim to further describe patient QoL after a bleed, while anticoagulated. Patients completing the interview will also be asked to provide any comments and opinions regarding the suitability of the chosen study PROMs for properly capturing all QoL issues after a diagnosis of AF.

Study Population:

Primary and secondary care patients with AF (aged ≥ 18) who are actively prescribed oral anticoagulant therapies (OATs) and have recently experienced bleeds, up to a maximum of 4 weeks prior to enrolment. No upper age limit will apply but potential study participants must match all inclusion/exclusion criteria, detailed fully in section 3.2.1 & 3.2.2.

Data Collection Methods:

Data sources: Electronic and/or paper records kept at primary and secondary care will be regularly searched for identification of suitable patients. Patients routinely attending anticoagulation clinics will be asked if they have experienced a recent bleed, and those who present as eligible will be asked to take part in the study. Posters placed in appropriate locations in GP clinics will encourage patients who have AF and are anti-coagulated to discuss minor bleeds with GPs. Lastly, e-cards will be sent out to patients with AF groups on forums, social media pages, web site and newsletters run by online AF support networks.

Exposure: Anticoagulated to prevent stroke following diagnosis of AF.

Data collection: Data will be obtained using questionnaires supplied on paper case report forms or via an electronic device, depending on participants' preference and up to date restrictions due to coronavirus outbreak in regards to using touchscreen devices. Data captured via an electronic device will be submitted directly to a REDCap database which has been designed for the study. Completed paper versions of the survey will later be transcribed into the database by a member of the study team. A random subset of enrolled AF patients will also undergo recorded interviews with research nurses in order to capture valuable free-form, emotive data regarding effect on quality of life after a bleed and to document patient opinion on current available PROMs used in the study.

Data Analyses:

Descriptive analysis of QoL reported by AF patients following a minor or major bleed while anticoagulated. Comparison to age-adjusted population norms may be insightful but no comparisons with controls are planned for this feasibility assessment, as no control patients will be enrolled.

Sample Size/Power:

Between 50 and 80 patients are expected¹, stratified into major and minor bleeds². Depending on recruitment efficacy, a maximum of 200 patients will be enrolled.

Limitations/Strengths:

The main limitation of the study is the lack of access to a suitable PROM, which specifically captures the true impact of bleeding on quality of life (QoL). The study will instead utilise previously validated generic and disease specific health-related quality of life (HRQoL) measures and compare them with population norms.

As this is a feasibility study it is unknown how successful chosen recruitment strategies will be for the study in the study sites and populations selected.

This study will enhance currently limited research into how bleeding specifically affects QoL in patients diagnosed with AF.

TABLE OF CONTENTS

TITLE PAGE 1

DOCUMENT HISTORY	3
RESEARCH REFERENCE NUMBERS	3
COVID-19 IMPACT STATEMENT	5
SYNOPSIS 6	
TABLE OF CONTENTS.....	9
1 INTRODUCTION.....	10
1.1 Study Rationale	10
1.2 Feasibility Questions.....	11
2 OBJECTIVES	12
2.1 Primary Objectives.....	12
2.2 Secondary Objectives	12
3 STUDY DESIGN	12
3.1 Overview of Study Design.....	12
3.2 Study Population.....	20
3.2.1 Inclusion Criteria	20
3.2.2 Exclusion Criteria	20
3.3 Data Source/Data Collection Process	21
3.3.1 Patient Reported Outcome (PRO) Measures	22
3.4 Definitions of Study Variables	23
3.4.1 Outcomes/Endpoint Variables	25
4 STATISTICAL ANALYSIS.....	25
4.1 Progression Criteria	26
5 STUDY LIMITATIONS/STRENGTHS	26
6 STUDY CONDUCT	27
6.1 Ethics Committee Review and Informed Consent.....	27
6.1.1 Ethics Committee Review	27
6.1.2 Informed Consent	27
6.2 Responsibilities within the Study.....	27
6.2.1 Sponsor Roles and Responsibilities	27
6.2.2 Principal Investigator Roles and Responsibilities	28
6.2.3 Steering Committee	28
6.3 Confidentiality of Study Data.....	28
6.4 Quality Control.....	29
6.5 Database Retention and Archiving of Study Documents	29
6.6 Registration of Study on Public Website	29
7 ADVERSE EVENT REPORTING	29
8 LIST OF ABBREVIATIONS	30
9 SCIENTIFIC PUBLICATIONS	31
10 REFERENCES.....	32

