2 OBJECTIVES

2.1 Primary Objectives

To test the feasibility of i) identifying and recruiting patients with both minor and major bleeds³² as a result of anticoagulant treatment for AF associated events, and ii) measuring their QoL in both primary and secondary care settings.

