3.2 Study Population

Adult patients (≥ 18) who have AF are actively prescribed oral anticoagulant therapies (OATs) and have recently experienced bleeds, up to a maximum of 4 weeks prior to enrolment. No upper age limit will be applied, but patients must match all other inclusion/exclusion criteria (section 3.2.1). Patients will be selected from the Swansea area only, who attend/have attended either anticoagulation clinics within the Swansea City Health Cluster, Morriston emergency department or have been admitted to wards at Morriston Hospital due to a bleed.

3.2.1 *Inclusion Criteria*

- Adult patients (≥ 18 years old)
- Patients who can understand all study information and literature to provide fully informed consent
- Atrial fibrillation (AF) as the primary diagnosis
- Having a major or minor bleed up to a maximum of 30 days prior to point of enrolment
- Receiving oral anticoagulation therapy for AF

3.2.2 *Exclusion Criteria*

- Pregnant women
- Patients with active cancer
- Patients unable to consent for themselves
- Patient on concomitant antiplatelet therapy

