4.1 Progression Criteria

The feasibility of the trial methods, recruitment strategies, and its potential to be further developed and into a full qualitative study will be measured on key progression criteria. These criteria have been approved by our Trial Steering Committee and study managers, where applicable:

- Minimum requirements met for recruitment (50 eligible patients)
- Retention of at least 50% of enrolled patients at follow-up
- 70% PROMs data completion at baseline and 40% completion of PROMs at follow-up

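### The synopsis declares the study feasible on 50 recruits alone although section 4.1 also measures feasibility on retention and PROM completion, and section 3.2 (Swansea only) conflicts with the online route on who may be enrolled and count towards the 50.

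*Protocol*

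**What the plan says.** **Feasibility rule.** The protocol synopsis, under primary outcome measures, says "The study will be considered feasible if recruitment efforts prove successful", and below it "A minimum of 50 patients recruited will deem the study as successful". The next primary bullet names the three PROMs but attaches no threshold to them.

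Section 4.1 opens with "The feasibility of the trial methods, recruitment strategies, and its potential to be further developed" and says these will be measured on a list of criteria. The first is the same minimum of 50, counted there as eligible patients. The others are "Retention of at least 50% of enrolled patients at follow-up" and "70% PROMs data completion at baseline and 40% completion of PROMs at follow-up".

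The primary objective in section 2.1 has two parts: (i) identifying and recruiting patients with bleeds, and (ii) "measuring their QoL in both primary and secondary care settings".

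**Population.** Section 3.2 states "Patients will be selected from the Swansea area only, who attend/have attended either anticoagulation clinics within the Swansea City Health Cluster", or the Morriston emergency department or wards. The synopsis (data sources), section 3.1 and section 3.3 (data sources) also recruit through online AF support networks. Section 3.1 adds a support-group database of about 60,000 patients, with consent, questionnaires and follow-up all handled digitally. The synopsis refers the reader to 3.2.1 and 3.2.2 for the full eligibility criteria, and neither list contains an area or site criterion.

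**The concern.** Both issues concern the number on which the headline conclusion rests.

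First, the synopsis and 4.1 each say what makes the study feasible, and they differ. A study that recruits 50 patients and then loses most of them is a success under one and misses a criterion under the other. Recruitment cannot show whether QoL can be measured, so the synopsis rule leaves part (ii) of the primary objective without a threshold. The choice between the two statements should not be left until the results show which is more favourable.

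Second, a person recruited online outside Swansea meets every listed inclusion criterion and follows a route that 3.1 describes in detail, yet falls outside 3.2. If such recruits count, the 50 may be reached partly through a route that does not test identification in primary and secondary care, which the primary objective names. If they do not count, 3.1 provides for enrolling patients whom 3.2 excludes.

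**Working it through.** **Inputs from the protocol.** Minimum 50, target 50 to 80, maximum 200 (synopsis and 3.1). Retention at least 50%; PROM completion 70% at baseline and 40% at follow-up (4.1). The 50 to 80 is taken from cited guidance with no power or precision calculation, so there is no formula to reproduce. The 50 itself is not in dispute.

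**Step 1: thresholds in patients.**

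| Enrolled | Synopsis needs | 4.1 retained (0.5 × n) | 4.1 baseline PROMs (0.7 × n) | 4.1 follow-up PROMs (0.4 × n) |
|---|---|---|---|---|
| 50 | 50 recruited | 25 | 35 | 20 |
| 80 | 50 recruited | 40 | 56 | 32 |
| 200 | 50 recruited | 100 | 140 | 80 |

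The PROM columns assume that the percentages are of enrolled patients; 4.1 does not state the denominator. The synopsis requirement stays at 50 recruits however many are enrolled.

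**Step 2: can the two disagree?** Yes. With 50 enrolled and 24 retained, retention is 24/50 = 48%. The synopsis rule is met and the 4.1 retention criterion is missed.

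**Step 3: how likely is that?** The protocol gives no expected retention, so the true rate p is assumed over a range, with patients independent. The chance of disagreement on retention is P(X ≤ k), where X is binomial(n, p) and k is one below the threshold (24, 39 or 99).

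| Assumed true retention | n = 50 | n = 80 | n = 200 |
|---|---|---|---|
| 40% | 90% | 96% | over 99% |
| 50% | 44% | 46% | 47% |
| 55% | 20% | 16% | 7% |
| 60% | 6% | 3% | 0.2% |
| 70% | 0.1% | 0.01% | under 0.01% |

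The baseline PROM criterion can separate the two statements as well. With 50 enrolled, the chance of reaching 35 completions is 10%, 57% or 97% if true completion is assumed to be 60%, 70% or 80%.

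**Step 4: the population statements side by side.**

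- Section 3.2: Swansea area only, through the cluster clinics, Morriston ED or Morriston wards.
- Synopsis, 3.1 and 3.3 (data sources): these settings plus online AF networks, with no area limit.
- Section 3.1: a database of about 60,000, filtered for eligible AF patients; no Swansea filter is mentioned.
- Sections 3.2.1 and 3.2.2: no area or site criterion.
- Section 3.3 (data collection): the list of how cases are identified names clinics, ward records and ED records, and omits the online route.

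An online recruit outside Swansea is therefore eligible under 3.2.1 and 3.2.2 and enrolled under 3.1, but excluded by 3.2. Because 4.1 counts eligible patients and the synopsis counts recruited ones, the protocol does not settle whether that person is one of the 50.

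**The case against.** The best defence of the synopsis is that it summarises and 4.1 supplies the detail. The sentence on 50 patients sits beneath the bullet on recruitment, so it can be read as defining recruitment success only. The PROMs appear in the next bullet, and the 50 is the same in both places. This explains how the wording arose but does not remove the conflict: the synopsis applies feasible and successful to the study as a whole. Nor does calling the 4.1 list progression criteria separate it from feasibility, because 4.1 says that feasibility itself is measured on it.

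The online route also has a legitimate place. The first feasibility question in 1.2 has no setting limit, and 3.3 says that the study will explore how best to find patients. Section 3.4 lists recruitment pathway among the variables to be reported in the descriptive analysis. This last point stands and reduces the harm considerably: a reader of the report should be able to see the split by route. It does not settle who is eligible.

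Three stronger readings are tempting and are not supported:

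- A reader might infer that most of the 50 would come from the online database because it is so large. Its 60,000 entries are unfiltered, and the protocol gives no yield for any route, so the share by route cannot be derived.
- A reader might treat the absence of a statement that all the 4.1 criteria must be met as a further error. Three bulleted criteria read naturally as cumulative, and how they combine may be set out in an analysis plan not shown here.
- A reader might take the probabilities above as a forecast. They rest on assumed retention and show only when the two statements would part.

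**Conclusion.** Both contradictions stand on the text, and both should be fixed. The synopsis success statement omits the retention and PROM-completion thresholds on which 4.1 measures feasibility, and the same data can satisfy one and miss the other. The practical size depends on a retention rate that the protocol does not give. Disagreement on retention is close to an even chance if true retention is near 50% and unlikely at 60% or above, particularly with more than 50 enrolled. The population conflict has no calculable size, but it leaves open who may count towards the primary threshold.

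Neither point shows that 50 is the wrong number or that the planned descriptive analyses are invalid. What is at stake is whether the study can state a single, pre-specified feasibility conclusion, including one for primary and secondary care.

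**What to change.** 1. Make the success rule in the synopsis the same as 4.1, so that it includes the retention and PROM-completion criteria as well as the 50.
2. Reconcile 3.2 with the synopsis, 3.1 and 3.3 on whether online recruits outside Swansea are eligible and count towards the 50. If they are, amend the area and site sentence in 3.2 and add the online route to the case-identification list in 3.3. If they are not, state the area limit where the online route is described.
3. If online recruits count, use the pathway data that 3.4 already commits to reporting, so that the feasibility conclusion for primary and secondary care is drawn from patients identified through those settings.

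The cost is wording in the synopsis and 3.2, and in 3.1 and 3.3 as needed; no new data are required. The downside is that success becomes somewhat harder to claim. On the retention criterion alone, with 50 enrolled, the added chance of falling short is 6% if true retention is 60% and 44% if it is 50%.

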1 INTRODUCTION

1.1 Study Rationale

Atrial Fibrillation (AF) is the most common cardiac arrhythmia. The overall prevalence of AF is reported to be 0.4-1%³. However, many clinicians debate the true global prevalence, stating that it is likely to be underestimated as many individuals are asymptomatic and possibly undiagnosed⁴. Rates of AF are also highest in patients aged over 60⁵. Previous studies have concluded that for males aged 75-79, rates of AF doubled in comparison to those aged 65-69⁶. As the general population continues to age, AF is likely to become much more of a public health burden⁷, with predicted numbers of AF patients estimated to reach a minimum of 1.3 million patients in the UK by 2060⁸.

Patients can develop further AF-related complications, for example, significant risks of stroke and systemic thromboembolism and increased mortality^{9 10}. Strokes triggered as a result of AF are a major complication in patients and are associated with significant morbidity and mortality¹¹.

The general symptom burden on AF patients and the subsequent reduced ability to undertake daily activities has been widely examined in numerous studies¹²⁻¹⁴. People living with AF have a much lower quality of life (QoL) than patients who do not have the disease^{11 15}.

With the steady increase in AF prevalence and its impact on patients, it is becoming increasingly necessary to deliver adequate treatment and/or therapies, which can improve health related quality of life (HRQoL) in patients. Identifying any underlying causes of AF may be the first step in any treatment plan¹⁶, as treating the cause may be enough to treat and rectify the related AF. Once a detailed history of the form¹⁷
¹⁸ and significance of AF in the patient is established, a treatment plan should then be considered¹⁹. Treatment plans usually involve controlling the heart rate or rhythm.

Oral anticoagulation therapies (OATs) (for example warfarin and apixaban) are prescribed in conjunction with rate management in order to limit the risk of stroke and systemic thromboembolism. They are, however, associated with the serious side effect of bleeding. These bleeding complications include intracranial, gastrointestinal, genitourinary and respiratory tract bleeding haematuria²⁰. Bleeding risk can be determined using calculated risk scores such as HAS-BLED²¹. A higher HAS-BLED score indicates that the patient is more at risk of a major bleed, which has previously influenced patient and clinician decisions not to offer or to withdraw anticoagulant treatment²². However, the European Society of Cardiology 2016 guidelines advise that it is better to treat with OATs (despite the risk of bleeding) than not use OATs²³.

Bleeding while anticoagulated is believed to have a significant impact on patient quality of life (QoL)²⁴. Quality of life and health status are considered to have a colinear relationship, but this is typically difficult to define. There are already a multitude of validated measures which attempt to quantify Health Related Quality of Life (HRQoL)²⁵⁻²⁷. HRQoL tools can also be disease- or injury-specific and aim to capture both benefits and undesirable aspects of different diseases from a patient perspective, including consequences of living with the disease²⁸. More and more focus is being directed towards improving patient reported quality of life when delivering quality and value-based healthcare^{29 30}.

There is currently limited research into how bleeding events impact QoL in AF patients, especially those who experience minor bleeds, for which no medical care is sought (as per Bleeding Academic Research Consortium (BARC) definition)³¹. Likewise, there are no existing and/or validated patient-reported outcome measures (PROMs) developed for use in assessing how bleeding influences patient QoL.

This feasibility study will examine how patient QoL is affected when they experience either a major or minor bleed, defined by the International Society on Thrombosis and Haemostasis (ISTH)³², while taking OATs for the management of AF.

